5.6 Concomitant and Excluded Therapy

Concomitant medications are any prescription medications or over-the-counter preparations used by the subject between 7 days prior to enrollment (30 days for anticoagulants) and 30 days following IUS discontinuation. All concomitant medications, including excluded therapies, must be documented in the Concomitant Medication CRF. Subjects who begin to chronically use excluded therapies may require discontinuation from the study. The Medical Monitor should be contacted to discuss possible discontinuation of these subjects.

The following concomitant therapies are excluded while on study treatment:

- Hormonal contraceptives with the following exceptions:
 - An oral, transdermal, vaginal or combined monthly injectable hormonal contraceptive may be used in the first month only as outlined in Section 6.3;
 - Emergency contraception should be recommended in any situation when the subject feels the IUS expelled and she subsequently had intercourse. Subjects will not be discontinued from the study because of emergency contraceptive use.
- A previously inserted contraceptive implant, IUD or IUS unless the implant, IUD or IUS is removed prior to study IUS insertion (may be removed immediately before study IUS insertion).
- Any other contraceptive method that could obscure the efficacy parameters of this investigational contraceptive should not be used during study participation. However, if the subject feels the need to protect herself against sexually transmitted infections, she should be advised to use a male condom. If the use of a male condom becomes a regular part of the subject's contraception, the site Principal Investigator should check with the Medical Monitor

about possibly discontinuing the subject from study participation. All condom usage will be documented on the daily subject diaries.

- Any non-contraceptive estrogen, progesterone, testosterone, or gonadotropin (e.g. hCG)
- Misoprostol on day before or day of IUS insertion or removal
- Any cervical dilating instrument used during IUS insertion other than Pratt dilators, a lacrimal duct probe or an os finder
- Any investigational treatment or medication other than the LNG20.

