- Removal of IUS, if not already expelled or removed (at an outside location)
- Retain all removed or expelled IUSs (when possible) per the Study Reference Manual
- Contraceptive counseling
 - Immediate initiation of another method in the office when possible
 - Request to use this method or be abstinent for at least one week to avoid conception within 7 days after IUS discontinuation
- Schedule next appointment

6.7 30-Day Safety Follow-Up

All subjects must have a safety follow-up visit between 30 and 43 days after the Treatment

Completion/Early Discontinuation Visit (except those made lost to follow up or who withdrew consent per section 7.18). If the subject contacts the office with an expulsion that was 30 or more days ago, this visit may be combined with the Early Discontinuation visit.

- Review of adverse events (note: all adverse events occurring within 30 days of IUS discontinuation should be reported on the appropriate adverse event CRF)
- Review of concomitant medications used up to 30 days of IUS discontinuation
- Menstrual history if not using a hormonal method of contraception
- High sensitivity urine pregnancy test (if positive, see Sections 7.4 and 7.5)
- Weight and blood pressure
- Additional contraceptive counseling if needed
- Review with subject that continued telephone or clinic follow-up (as appropriate) is indicated for the following:
 - an ongoing IUS-related adverse event at study discontinuation should be followed monthly until the adverse event resolves or has stabilized
 - any subject electing to use a non-hormonal contraceptive method or no contraception (including those desiring pregnancy) will be followed monthly for up to 3 months after IUS removal/expulsion for return of menses. Any woman who does not menstruate within 3 months following IUS discontinuation will be referred for appropriate evaluation and continue to be followed monthly until menses has occurred or a diagnosis for the cause of the secondary amenorrhea has been established
- Those women desiring a pregnancy after IUS discontinuation will be contacted every three months from their Treatment Completion/Early Discontinuation Visit up to one year to record return to fertility.
 - Once a pregnancy is reported no further follow-up contact is required.
 - Women who do not become pregnant and change their intention before completing a full 12 months of follow-up will be discontinued from the study and not be included in the return to fertility cohort.

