5.3.4 Missing Concomitant Medication Start and Stop Dates

For concomitant medications (CM), the following rules for imputing values for missing start dates are used:

- If the CM start date field includes a SAS missing value or is completely missing, the start date is set to the IUS insertion attempt date.
- If the CM start date field is missing day only, set it equal to the first day of the recorded month and year.
- If the CM start date field is missing day and month only, set it equal to the first day of January of the recorded year.
- If the CM stop date field includes a SAS missing value or is completely missing, the stop date is set to the last date of known product use.
- If the CM stop date field is missing day only, set it equal to the 15th day of the recorded month and year
- If the CM stop date field is missing day and month only, set it equal to the 31st day of December of the recorded year.
- If the CM stop date field is missing month only, set it equal to December of the recorded year
- Any imputed CM stop date that is before the insertion attempt date implies the CM was a Pre-Trial Medication. Any medication started on or after the insertion attempt date or any medication started before insertion but ending on or before the last known date of product use is a Concomitant Medication.

5.3.5 Missing Dates for Other Events, Including Return to Menses, Return to Fertility, Pap Tests, Date of IUS Expulsion/Removal, and Reported Pregnancies

For missing dates of other events, any date that is completely missing or contains the year only will be set to the date of the subject's last clinic visit. If a month and year are recorded but the day is unknown, the day will be set to the first day of the month. If this

results in an imputed date that is earlier than the last clinic visit, the date will be set to the date of the last clinic visit.

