8. TREATMENT AND MEDICATION

8.1 Pre-trial and Concomitant Medications

Verbatim terms on eCRFs will be mapped to the narrowest Anatomical/Therapeutic/Chemical (ATC) class possible and generic drug names using the World Health Organization (WHO) Drug Dictionary Enhanced (DDE). For example, if the 4th level is not available, then the 3rd level (pharmacological subgroup) will be provided.

Concomitant medications include any medication or health product (any prescription medications or over-the-counter preparations) taken during the active study treatment period. Pre-trial medications include any medications taken within seven days (30 days for anticoagulants) of enrollment. Concomitant medications will be summarized for each treatment group by WHO ATC class and generic drug name. These summaries will present the number and percentage of subjects using each medication. Subjects may have more than one medication per ATC class and Generic Drug Name. At each level of subject summarization, a subject is counted once if she reported one or more medications at that level. Each summary will be ordered by descending order of incidence of ATC class and generic drug name within each ATC class.

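### The medication rule in SAP 5.3.4 does not match use during treatment: drugs started after IUS removal count as concomitant, and some drugs taken throughout use fall out

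*SAP*

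**What the plan says.** SAP 5.3.4 first imputes medication dates and then classifies the medication. When the stop date is "completely missing, the stop date is set to the last date of known product use". A stop date lacking only the day goes to the 15th of the month, and one known only to the year goes to 31 December. The last bullet then classifies:

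- Pre-trial: "Any imputed CM stop date that is before the insertion attempt date implies the CM was a Pre-Trial Medication".
- Concomitant, first limb: "Any medication started on or after the insertion attempt date".
- Concomitant, second limb: "any medication started before insertion but ending on or before the last known date of product use is a Concomitant Medication".

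SAP 8.1, which specifies the table, uses a different definition. Concomitant there means "taken during the active study treatment period", and "Pre-trial medications include any medications taken within seven days (30 days for anticoagulants) of enrollment". Protocol 9.6 agrees with SAP 8.1 and says the two classes are presented separately.

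Protocol 5.6 gives a third definition. Its window opens 7 days before enrollment (30 for anticoagulants) and closes "30 days following IUS discontinuation". It requires everything in that window, excluded therapies included, to be entered on the Concomitant Medication form. At the discontinuation visit, Protocol 6.6 asks for "Immediate initiation of another method in the office when possible".

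**The concern.** A table of concomitant medication should show what women took while the IUS was in place. The test for that is overlap with the period of use. SAP 5.3.4 instead tests the start date alone for one group of drugs, and a one-sided stop date for the other.

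The clearest consequence concerns contraception. Protocol 5.6 excludes hormonal contraceptives during study treatment, apart from limited exceptions. A woman who starts one after removal, within the collection window, would still appear in a table that SAP 8.1 describes as use during treatment. Her entry could not be told apart from permitted first-month use or from excluded use alongside the IUS. In the other direction, some therapy taken for the whole period of use would be missing. SAP section 1 gives the SAP precedence over the protocol, but that does not settle the matter, because the SAP disagrees with itself.

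**Working it through.** The plan states no figure on this point, so the check is date logic. Set the insertion attempt and enrollment at day 0, and removal (also the last known date of use) at day 1000. Write s for start and e for stop after imputation.

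- SAP 5.3.4 concomitant: s ≥ 0, or (s < 0 and e ≤ 1000).
- SAP 5.3.4 pre-trial: e < 0. The sentence mentions imputed dates only; I take it to cover recorded ones too.
- SAP 8.1 concomitant: s ≤ 1000 and e ≥ 0, with an ongoing drug having no upper limit on e.
- SAP 8.1 pre-trial: use in days −7 to 0.

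| Case | Start | Stop | SAP 5.3.4 | SAP 8.1 |
|---|---|---|---|---|
| A | −20 | −3 | pre-trial and concomitant | pre-trial only |
| B | −20 | 500 | concomitant | concomitant, pre-trial |
| C | −20 | 1010 | neither | concomitant, pre-trial |
| D | −20 | missing, set to 1000 | concomitant | concomitant, pre-trial |
| E | 100 | 200 | concomitant | concomitant |
| F | 100 | 1010 | concomitant | concomitant |
| G | 100 | missing, set to 1000 | concomitant | concomitant |
| H | 1000 | missing, set to 1000 | concomitant | ambiguous (removal day) |
| I | 1005 | 1020 | concomitant | not concomitant |
| J | 1005 | missing, set to 1000 | concomitant, with stop before start | not concomitant |

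**Started after removal (I, J).** Both meet the first limb, since 1005 ≥ 0 and nothing bounds it above. Both fail SAP 8.1, since 1005 > 1000. In J the imputed stop is 1005 − 1000 = 5 days before the start. The adverse event rules in SAP 5.3.3 correct a stop date earlier than the start; SAP 5.3.4 does not.

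**Started before insertion, stopped after last use (C).** The second limb fails because 1010 > 1000, the first because −20 < 0, and the pre-trial test because 1010 > 0. The drug was taken throughout use and has no class. Partial dates add cases. With removal on 10 June, a stop date recorded only as June becomes 15 June, which is after 10 June. A stop date known only to that year becomes 31 December. Either would drop a drug started before insertion.

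**What is kept (D, F, G).** A completely missing stop date becomes day 1000 and meets e ≤ 1000. A drug started during use meets the first limb whatever its stop date.

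**Stopped before insertion (A).** Since −3 ≤ 1000, the second limb is met literally, although the preceding sentence makes the drug pre-trial.

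**Alternative reading.** Suppose the clause on ending by last use governs both limbs, so that concomitant means e ≤ 1000. Case I is then correctly left out (1020 > 1000), but F is lost (1010 > 1000), C is still lost, and A and J are still wrong. The repetition of the words for any medication favors the two-limb reading, and neither reading reproduces SAP 8.1.

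**The case against.** Several points on the other side stand.

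- A reader might infer that the rule drops chronic therapy in general. It does not, as cases D, F and G show. Medication review ends 30 days after discontinuation, and a long-term drug still being taken then would usually have no stop date. Case C should therefore be uncommon.
- Protocol 5.6 itself counts medication up to 30 days after discontinuation as concomitant, so including drugs started after removal agrees with one definition in the documents. This does not clear the SAP, whose own table definition in 8.1 is narrower. It does mean that three definitions need reconciling.
- A reader might infer harm to the Pearl Index. SAP 5.5 takes other-contraceptive use for cycle exclusion solely from the daily diaries, so the medication class does not enter it.
- A reader might infer that the per-protocol population is affected. No section ties major deviations to this class, and SAP 9.3 says that use of another method does not by itself exclude a woman from that population.
- Hormonal contraceptives will appear in the table legitimately, because Protocol 5.6 and 6.3 allow certain methods to continue into the first month. That is true, but it makes it more useful to keep post-removal starts out of the same row.
- The double classification in case A disappears if the two sentences are read together. It is a flaw of wording, easily closed.

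**Conclusion.** The point holds as an inconsistency in a stated rule with a limited effect. The last bullet of SAP 5.3.4 contradicts SAP 8.1 and Protocol 9.6 in two respects: it has no cut-off at removal, and it loses drugs started before insertion whose stop date falls after last use. It also overlaps with the pre-trial class when read literally.

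The effect is confined to the descriptive medication tables. The documents give no share of women who start a hormonal method within 30 days of removal, so no headcount can be supported. The appearance of replacement contraceptives in the table assumes that sites enter them on the medication form, as Protocol 5.6 implies. The statement that ongoing drugs are kept assumes they are stored with a missing stop date; the form is not in the documents. It is worth correcting because the table would otherwise not show what its definition says it shows.

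**What to change.** Replace the last bullet of SAP 5.3.4 with an overlap rule:

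- **Concomitant:** started before the IUS removal or expulsion date (or, if the IUS is still in place, on or before the last known date of use), and either stopped on or after the insertion attempt date or ongoing.
- **Pre-trial:** any use within 7 days (30 for anticoagulants) before enrollment, as in SAP 8.1. A drug stopped before insertion is pre-trial only.
- **Post-treatment:** started on or after the removal or expulsion date, tabulated separately.
- **Imputed dates:** a partial stop date imputed to a day after last use does not remove a drug from the concomitant class. An imputed stop date earlier than the start date is set equal to the start date, as SAP 5.3.3 does for adverse events.
- **Scope:** state that this definition governs the tables, in place of the wider collection window in Protocol 5.6.

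The strict inequality at removal matters. SAP 5.4 counts use through the removal date, so a rule of starting on or before last use would still class a contraceptive begun at the removal visit (case H) as concomitant. One side effect is that a drug given on the removal day for the procedure itself also falls in post-treatment, and the SAP should say so.

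Under this rule, cases B to G are concomitant, A is pre-trial only, and H to J are post-treatment. The cost is one SAP paragraph, one derivation and one additional table, with no new data. It should be done before the next data cut-off, because SAP 5.1 treats analyses performed after a cut-off as post hoc.

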5.4 Standard Calculations

Variables requiring calculation will be derived using the following formulas:

- **Study day** – For a given date (*date*) on or after successful IUS insertion (*iusindt*), study day is calculated as:

$$\text{Study day} = \text{date} - \text{iusindt} + 1$$

For a given date (*date*) prior to successful IUS insertion (*iusindt*) or for subjects with failed insertion, study day is calculated as:

$$\text{Study day} = \text{date} - \text{iusindt}.$$

The day of successful IUS insertion is Study Day 1 and the day prior to IUS insertion is Study Day -1. There is no Study Day 0

Months – A duration expressed in months is calculated as the number of completed calendar months plus the proportion of any partial month completed. A month is calculated using the following formula: Duration in months = (date2-date1)/30.4

- **Years** - A duration expressed in years between one date (*date1*) and another later date (*date2*) is calculated using the formula noted below:

$$\text{Duration in years} = (\text{date2}-\text{date1})/365.25$$

- **Age** - Age is calculated as the number of years from the date of birth (*DOB*) to the IUS insertion attempt date (*iusindt*). For displaying a subject's age, the following formula is used:

$$\text{Age (years)} = \text{floor}(\text{insertion attempt date} - \text{birthdate})/365.25$$

- **Body Mass Index (BMI)** - BMI is calculated using height (in cm) and weight (in kg): $\text{BMI (kg/m}^2\text{)} = \text{weight (kg)} / [\text{height (cm)} / 100]^2]$

- **Cycles of Use** – Cycles are calculated using the date the IUS was expelled/removed (from the IUS Discontinuation CRF). Total use duration expressed as the number of 28-day cycles is defined as (IUS expulsion/removal date - date of IUS insertion (*iusindt*)+1)/28. If the expulsion/removal date is unknown then:

- Subjects who are still on treatment will have their last known date of product use used in the cycle calculations in lieu of an IUS expulsion/removal date, derived as follows: For the evaluation of safety, the last known date of product use will be the last date of on-study contact with the subject where she reported that the IUS is still in place or the last date at which a pregnancy

test was performed (at study site or outside laboratory with copy of report), whichever is later. For the evaluation of efficacy, the last date at which a pregnancy test was performed will be used (at study site or outside laboratory with copy of report).

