9.1 Pregnancy on Study

For all pregnancy analyses, pregnancy is defined as occurring when a positive urine or blood pregnancy test is reported. Confirmation of pregnancy should be attempted by the study site and may include:

- urine pregnancy test at the study site
- serum quantitative hCG (at study site or report)
- ultrasound examination confirming a pregnancy (at study site or report)
- a surgical procedure for treatment of an extrauterine pregnancy or intrauterine pregnancy (report)

A pregnancy is considered to have occurred "on treatment" if a test or examination confirms a pregnancy and with a date of conception while the IUS is being used as a method of contraception by the subject up to and including 7 days after IUS discontinuation. Pregnancies solely reported by the subject that cannot be verified by any means of examination or follow-up reporting will be evaluated for determination of whether they should be classified as "on treatment" or "not on treatment" for the MITT and PP efficacy evaluations. All reported pregnancies, even if not confirmed by the site, will have a Pregnancy Narrative completed by the study investigator.

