10.2.2 Pregnancy Rates

Life table methods will be used to estimate the overall pregnancy rate for each year and the cumulative pregnancy rate after each year. Both uterine and ectopic pregnancies will be included. Pregnancy dating and confirmation will be determined by medical assessments, including ultrasound examination. Confirmed pregnancy is the failure outcome and the corresponding time to pregnancy is the failure time. Time to pregnancy will be calculated as the date of conception minus the date of IUS insertion plus one (partial or completely missing conception dates handled per Section 5.3.5). Subjects who do not get pregnant will be censored at the last pregnancy assessment and failure time will be calculated as the date of the last pregnancy assessment minus the date of IUS insertion plus one.

Additionally, an overall Ectopic Pregnancy (EP) rate will be calculated as EP Rate per 100 Woman Years (WY) for the duration of use:

Number of EPs/WYs (number of 28-day cycles) = $x/100$ WY. The number of 28-day cycles per subject is not to exceed the duration of use being evaluated.

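### SAP 5.3.5 moves a partly dated expulsion, removal or conception to the last clinic visit even when that visit came after the event, so the recorded month is lost

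*SAP*

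**What the plan says.** SAP 5.3.5 deals with incomplete dates for a further list of items: "Including Return to Menses, Return to Fertility, Pap Tests, Date of IUS Expulsion/Removal, and Reported Pregnancies". It has three parts:

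- Wholly missing or year-only dates: "any date that is completely missing or contains the year only will be set to the date of the subject's last clinic visit".
- Month and year known: "If a month and year are recorded but the day is unknown, the day will be set to the first day of the month".
- Override of the second part: where it gives "an imputed date that is earlier than the last clinic visit, the date will be set to the date of the last clinic visit".

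SAP 10.2.2 carries the rule into time to pregnancy: "partial or completely missing conception dates handled per Section 5.3.5". Expulsion and removal dates enter the time-to-event formula in SAP 11.9, and menses dates enter the one in SAP 11.11.

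Expulsion and removal dates also enter Pearl Index exposure through SAP 5.4: "Cycles are calculated using the date the IUS was expelled/removed (from the IUS Discontinuation CRF"). That section has its own rules for an unknown expulsion or removal date. When a woman reports that the IUS is gone, for example, they use the later of the day before that contact and the last pregnancy test.

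SAP 9.1 calls a pregnancy on treatment if it is confirmed "with a date of conception while the IUS is being used as a method of contraception by the subject up to and including 7 days", those days being counted from discontinuation of the IUS. Protocol 6.7 states: "All subjects must have a safety follow-up visit between 30 and 43 days after the Treatment" (that is, after the visit at which treatment is completed or stopped early).

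**The concern.** The override has no time limit. The subject's last clinic visit is the final one on file, not the last before the event. An expulsion, an outside removal or a conception during use is normally followed by a discontinuation visit and then a safety visit, so the first of the recorded month will usually be earlier than the last clinic visit. The override then applies, and a date with a known month gets the same value as a date with no information.

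The rest of the SAP does not work this way. The adverse event and medication rules in 5.3.3 and 5.3.4 keep the recorded month when only the day is missing, apart from bounds at the insertion attempt and the event's own start date.

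Partial dates are foreseeable. The protocol provides for expulsions of unknown date (7.7), expulsions reported 30 or more days later (6.7), and removal elsewhere or by another provider (6.6, 7.13).

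At stake are the expulsion and removal curves, time to pregnancy, the year of use to which an event is assigned, and the timing of menses that return before the safety visit. Possibly at stake too is whether a pregnancy counts as on treatment.

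**Working it through.** The plan attaches no figure to this rule, so there is none to reproduce. I applied the text literally and then scaled the consequences.

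**1. The rule.** Let F be the first of the recorded month and V the last clinic visit. The imputed date is V if F < V, and otherwise F.

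**2. Illustrative expulsion.** Recorded as March 2014; discontinuation visit 12 May; safety visit 18 June (37 days later, inside the 30 to 43 day window).
- F = 1 March, V = 18 June, so the imputed date is 18 June.
- The true date lies between 1 and 31 March, so the delay is 109 to 79 days, or 3.9 to 2.8 cycles of 28 days.
- If the two visits are combined, as Protocol 6.7 allows for an expulsion 30 or more days old, V = 12 May and the delay is 72 to 42 days (2.6 to 1.5 cycles).
- If V meant the last visit before the event, the result would be 1 March, or 10 March if a visit took place that day. The recorded month would be kept.

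**3. Menses, with V = 18 June.** Menses recorded for May would move to 18 June, which is late. Menses recorded for July would be set to 1 July, which is on time or early. Only menses before the safety visit are systematically delayed.

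**4. On-treatment test.** A conception date moved to the safety visit falls 30 to 43 days after the discontinuation visit. If that visit is the discontinuation date, the conception fails the 7-day limit. Conversely, a delayed expulsion date can bring a conception after the true expulsion inside the limit.

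**5. What one pregnancy is worth.** Inputs from SAP 4: 1,600 women; discontinuation of 20%, 19% and 17% in years 1 to 3, then 16% per year; 0.6 months lost per woman in year 1 and 0.3 per year later. Assumption: discontinuations are spread evenly over each year.
- Year 1: 1,600 × (1 + 0.80)/2 − 1,600 × 0.6/12 = 1,440 − 80 = 1,360 woman-years, or 17,680 cycles. One pregnancy = 100/1,360 = 0.07.
- Expected year 1 pregnancies at an index of 0.280: 0.280 × 13.60 = 3.8.
- Going from 4 to 3 moves the index from 1300 × 4/17,680 = 0.294 (exact Poisson upper limit 0.753) to 0.221 (upper limit 0.645), a fall of 25%. The distance to the upper limit goes from 0.46 to 0.42, well inside 1 unit in both cases.
- Year 10 as stated in Protocol 9.1, at least 350 woman-years: 100/350 = 0.29.
- Year 10 from the annual rates: 1,600 × 0.80 × 0.81 × 0.83 × 0.84⁶ = 302 women start and 302 × 0.84 = 254 finish, so (302 + 254)/2 − 302 × 0.3/12 ≈ 271 woman-years, and 100/271 = 0.37. These rates compound to 84.1% over 10 years, against the stated 76%, which is why this figure falls below 350.

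**6. Exposure added in year 1.** Assumptions: 3.1% to 4.5% expelled (the one-year range in Protocol 7.1.3); 10% to 100% of those with the day missing; 1 to 7.4 months added each (7.4 = 6 months between visits + 43/30.4).
- Low: 1,600 × 0.031 × 0.10 × 1 × 30.4/28 = 5 cycles (0.03% of 17,680).
- High: 1,600 × 0.045 × 1.00 × 7.4 × 30.4/28 = 578 cycles (3.3%).
- At worst, the index moves from 0.280 to 0.280 × 17,680/18,258 = 0.271. SAP 5.5 then takes the smaller of the date-based and diary-based counts, which reduces the effect further.

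**The case against.** The best defence is that the drafter meant the last visit before the event, which makes the rule a sensible floor. The literal reading can even date a conception after the test that revealed it, which points to a slip in drafting. That is plausible, but the SAP does not say it, a programmer would code what is written, and SAP 1 gives the SAP precedence over the protocol on analysis.

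Several limits on the reach of the rule stand:

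- **Conception dates.** Protocol 7.4 requires serum hCG at once and an ultrasound within 3 days of a positive test, so a partial conception date should be uncommon.
- **The numerator.** The cross-reference to 5.3.5 is in the time-to-pregnancy formula of SAP 10.2.2, not in the on-treatment definition of 9.1, which has unverifiable pregnancies evaluated for classification. Where the removal date is unknown and the IUS was in place, 5.4 makes conception the last date of use, so the pregnancy stays on treatment.
- **Removals.** Those done at the site take place at a clinic visit and will seldom lack a day.
- **Life table.** Women who do not conceive are censored at their last pregnancy assessment, so a moved expulsion date does not touch them.

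Two stronger inferences are tempting and do not hold. A reader might conclude that return to fertility would look slower. Fertility is followed by phone contacts every three months (Protocol 6.7, Appendix A), so most of these pregnancies come after the last clinic visit. A month-only date then goes to the first of the month and a wholly missing one goes back to the safety visit, both early rather than late. A reader might also expect Pap results to be affected, but SAP 11.13.3 only tabulates them by visit and no time-to-event estimate uses the date.

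**Conclusion.** The point holds as a defect in the written rule. Applied literally, 5.3.5 discards the recorded month for most partly dated expulsions, outside removals and on-treatment conceptions, with delays of about 6 to 16 weeks in the example (42 to 109 days). The firm consequences are wrong dates in the expulsion and removal curves, in time to pregnancy and year of use, and for menses that return before the safety visit.

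The effect on the Pearl Index is conditional. A reader might infer that the rule routinely removes pregnancies from the primary numerator. The documents do not support that: it requires a partial or missing conception date, a known discontinuation date, and use of the imputed date in the 7-day test, and the error can go either way. If it happened once, it would be worth about 0.07 units in year 1 and 0.29 to 0.37 in year 10. Nor does the rule inflate exposure materially: at the extreme of the assumed ranges the year 1 index falls from 0.280 to 0.271 before the diary limit.

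The documents do not give the number of partial dates, so the total effect cannot be fixed. The overlap between 5.3.5 and 5.4 is also unresolved, since the SAP does not say whether a partial expulsion or removal date counts as unknown.

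**What to change.** Make four changes, all in the SAP:

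1. In the 5.3.5 override, replace the last clinic visit with the last clinic visit before the event at which the IUS was verified in place or, for conception, at which the pregnancy test was negative.
2. Keep every imputed date inside the recorded month where there is one, and never later than the date the event was reported or detected. This also covers menses, for which IUS verification has no meaning.
3. State whether 5.3.5 or 5.4 governs a partial or missing expulsion or removal date.
4. Add a sensitivity analysis that counts a pregnancy with an imputed conception date as on treatment whenever its possible interval includes on-treatment days.

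Reporting how many dates of each type were imputed would let a reader judge the effect. The cost is a few sentences, a small change to the date-derivation program and one extra Pearl Index calculation. No new data are needed.
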